5.3.1 Dizziness Handicap Inventory

The DHI is a validated, self-report questionnaire. To assess the impact of impairment, the patients are asked to fill out the 25 item DHI questionnaire. The scale has three sub-domains (physical, functional, and emotional questions).

5.3.2 Posturography

Posturography is used to assess regulation of stance and gait.

5.3.3 EQ-5D-5L

The EQ-5D-5L is a self-administered questionnaire for evaluating QoL.

In patients suffering from FD due to increased rates of psychiatric comorbidities:

5.3.4 Patient Health Questionnaire Depression Module (PHQ-9)

The Patient Health Questionnaire depression module (PHQ-9) is an established instrument for the assessment of depression which is often associated with FD and is validated in German language.

5.3.5 Generalized Anxiety Disorder Scales (GAD-7)

The Generalized Anxiety Disorder Scales GAD-7 is an established instrument for the assessment of anxiety which is often associated with FD.

In patients suffering from BVP:

5.3.6 Video-Head Impulse Test

The vHIT is performed to evaluate the function of the VOR in the high frequency range for the horizontal semicircular canals. The test is based on the clinical head impulse test and it is a non-invasive and easy to perform, quick test that does not generate unpleasant vertiginous or nauseating sensation for the patient.

5.3.7 Caloric Testing

Caloric testing is used to quantify the function of the VOR in the low-frequency range of the horizontal semicircular canal on each side. After a lesion of the eardrum has been ruled out, the patient's head is positioned at an angle of 60° so that the horizontal semicircular canal is approximately vertical, thus ensuring maximum caloric excitability. Each external acoustic canal is then irrigated separately under standardized conditions with cool (30°C) and warm (44°C) water, while horizontal and vertical eye movements are recorded using electronystagmography.

5.3.8 Safety

Safety data will be collected in this study.

Clinical safety will be addressed by assessing AEs, physical examinations and vital signs in a descriptive manner.

As AEs and relevant medical history will not be coded with MedDRA, they will not be grouped by MedDRA preferred terms.

As previous and concomitant medication will not be coded with the World Health Organization Drug Dictionary, they will not be grouped to the Anatomic Therapeutic Chemical index.

5.3.9 Further Endpoints

Product complaints, Vertigoheel administration details (daily dose, change of dose), early termination, alcohol and drug consumption, smoking status.

5.4 Data Analysis

SAS or R software, or an equivalent software package will be used for statistical analysis.

Descriptive statistics will be provided for all parameters. The statistics will be appropriate for the type of data:

- For continuous and count variables, statistics will include the number of observations, mean, standard deviation, median, minimum, maximum, and two-sided 95% confidence interval (CI).

- For categorical variables, the descriptive statistics will include the count and percent of observations in each category along with its Clopper-Pearson two-sided 95% CI. The denominator for the percentage calculation will be based on the number of patients in the analysis population.

This is a non-interventional, observational study, therefore only CI are calculated. All endpoints will be analyzed by the appropriate type of descriptive statistic(s) as described above.

All variables will be analyzed in an exploratory manner. No formal statistical hypothesis testing will be performed.

Missing values will not be imputed.

The following subgroups will be defined:

- Patients with FD
- Patients with BVP

It is planned to include 20 patients with BVP and 40 patients with FD.

No further subgroups will be defined.

Shift tables for physical examination, DHI, Posturography, and vHIT will display the number and percentage of patients per baseline value category vs. the worst value category post-baseline

5.5 Populations for Data Analysis

The Intention-to-treat (ITT) population includes all patients who have received at least one dose of Vertigoheel® and have at least one post-baseline measurement.

As data collection will be based on routine clinical practice so that no stipulations will be made on assessments as well as on study visits, a per-protocol population will not be defined. Protocol deviations (as far as known), e.g. deviations from the in-/exclusion criteria, will be listed.

The Safety population (SP) includes all patients who have received at least one dose of Vertigoheel®.

Effectiveness analyses will be performed with the ITT population, safety analyses with the Safety population.

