Milestones	
 
under observation.
 
Unwilling or unable to comply with all the requirements of the study protocol.
 
Any relationship of dependence with the sponsor or with the investigator.
 
Sept 21 FPI, July 22 LPO, DBL Aug 22.
 

Statistical Methods	
 
Previous trial with Vertigoheel®
 
Weiser et al. (1998) The efficacy and safety evaluation of Vertigoheel® vs betahistine hydrochloride demonstrated a reduction of 2 score points of the mean intensity of vertigo attacks with a standard deviation of 0.8 score points and a non-inferiority limit of 20%. Power: 80%.
 
Current study
 
Significance level 0.05 (2-sided)
 
95% confidence intervals will be calculated to estimate treatment effects
 
Standard deviation of 0.8 for both indications
 
Lost to follow-up 10% (BVP) or 20% to 30% (FD) Power: 80%
 
(Please see 8.1)
 

Sample Size Calculations and Power Calculations	Sample size calculations have been performed for confidence intervals for different paired means. When the sample size is 20, a two-sided 95% CI for the difference between paired means will extend 0.351 from the observed difference in means. For a smaller CI a higher n is needed, i.e. $n=25$ (28 with 10% drop-out) distance from mean to limit 0.314, $n=30$ (33 with 10% drop-out) distance from mean to limit 0.265, n=40 (44) – 0.248.

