### **3.2 STUDY POPULATION**

Patients with BVP and FD will be recruited from the Department of Neurology in the German Center for Vertigo and Balance Disorders at the Hospital of the LMU, Munich.

As this is a prospective, non-interventional study, the study population will be composed of male and female patients, aged between 18 and 80 years old, diagnosed with BVP or FD. There are no specific patient withdrawal criteria for this non-interventional study except for the common ones such as loss of market authorization. A patient who is enrolled but does not complete the observational period may be replaced if study entry by end-April 2022.

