5.1 Sample Size Calculation

Sample size calculations were performed for confidence intervals for different paired means. When the sample size is 20, a two-sided 95% CI for the difference between paired means will extend 0.351 from the observed difference in means. For a smaller CI a higher n is needed, i.e. n=25 (28 with 10% drop-out) distance from mean to limit 0.314, n=30 (33 with 10% drop-out) distance from mean to limit 0.265, n=40 (44) – 0.248.

- Significance level 0.05 (2-sided)
- 95% confidence intervals will be calculated to estimate treatment effects
- Standard deviation of 0.8 for both indications
- Lost to follow-up 10%
- Power: 80%

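### The population called ITT is an observed-case set, and nothing planned shows whether treated patients lost before follow-up differ or how far they could move the DHI change

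*SAP*

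**What the plan says.** - **Analysis set.** Protocol section 8 (Populations for Data Analysis) and SAP 5.5 define ITT as patients with at least one dose who also "have at least one post-baseline measurement". The measurement need not be a DHI. All effectiveness analyses use this set. The Safety population requires only a dose.
- **Visits.** The flow charts (Protocol section 5, SAP section 4) schedule one post-baseline visit, at month 2±1.
- **Missing data.** SAP 5.4: "Missing values will not be imputed". No missing-data sensitivity analysis appears there or in SAP Appendix 1.
- **Early stopping.** Protocol 6.4 asks for the final-visit assessments when a patient discontinues or withdraws early.
- **Replacement.** Protocol 3.2: "A patient who is enrolled but does not complete the observational period may be replaced", subject to a study-entry limit of end-April 2022. SAP 3.2 does not carry this sentence.
- **Expected loss.** The Observational Plan Summary ("Lost to follow-up 10% (BVP) or 20% to 30% (FD") gives a separate, higher FD rate. Protocol section 8 and SAP 5.1 give 10% with no FD rate.
- **Tables.** In SAP Appendix 1, 14.1.2 (early termination) and 14.1.3 (population counts and reasons for exclusion) cover all patients. Demographics (14.1.6), primary diagnosis (14.1.8.1) and DHI (14.2.1) are restricted to ITT.

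**The concern.** With a single scheduled follow-up, the post-baseline condition largely selects the patients who came back. The study is open-label and has no comparator, so the mean DHI change and its interval are the main result. If return is related to how the patient fared, that selection passes directly into the estimate. A reader who sees ITT will assume that treated patients were kept in.

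The planned tables would show how many patients were excluded and why. They would not show whether those patients had a different age, diagnosis or baseline DHI, because the tables carrying that information are limited to the selected set. Nothing indicates how sensitive the mean change is to the missing patients.

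The any-measurement criterion adds a second problem. A patient with, say, follow-up posturography but no follow-up DHI is in the ITT set and stays in the percentage denominators that SAP 5.4 bases on the analysis population, yet contributes no DHI change.

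**Working it through.** **Inputs.** Planned size, SAP 5.4: "It is planned to include 20 patients with BVP and 40 patients with FD". SD, SAP 5.1: "Standard deviation of 0.8 for both indications". Two-sided 95% interval, SAP 5.1. Loss rates as quoted above.

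**Step 1: reproduce the plan's precision.** Half-width = 1.96 × SD / √n.
- n = 20: 1.96 × 0.8 / √20 = 0.351. The plan says that the interval "will extend 0.351 from the observed difference in means", so this agrees.
- n = 40: 1.96 × 0.8 / √40 = 0.248, which also agrees.

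The plan's figures therefore refer to patients with an observed change. (The stated 0.265 at n = 30 does not reproduce; the formula gives 0.286. That is a separate matter.)

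**Step 2: patients without a follow-up DHI, no replacement.** Missing = n × d. The half-width is recomputed on those remaining, with the plan's SD of 0.8.

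| Group | Loss d | Missing | Observed | Half-width |
|---|---|---|---|---|
| FD | 10% | 40 × 0.10 = 4 | 36 | 0.261 |
| FD | 20% | 40 × 0.20 = 8 | 32 | 0.277 |
| FD | 30% | 40 × 0.30 = 12 | 28 | 0.296 |
| BVP | 10% | 20 × 0.10 = 2 | 18 | 0.370 |

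Across both groups this is 4 + 2 = 6 of 60 (10%) at the SAP rate, or 10 to 14 of 60 (17% to 23%) at the summary's rates. The SD of 0.8 comes from a vertigo-intensity score in the earlier trial that the plan cites, so the half-widths show relative widening, not DHI precision.

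**Step 3: effect on the mean.** Let f be the mean change in lost patients divided by the mean change in observed patients. Then

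all-treated mean / observed mean = (1 − d) + d × f.

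The documents give no value for f, so a range is shown.

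| Loss d | f = 1.5 | f = 1 | f = 0.5 | f = 0 | f = −0.5 |
|---|---|---|---|---|---|
| 10% (FD or BVP) | 1.05 | 1.00 | 0.95 | 0.90 | 0.85 |
| 20% (FD) | 1.10 | 1.00 | 0.90 | 0.80 | 0.70 |
| 30% (FD) | 1.15 | 1.00 | 0.85 | 0.70 | 0.55 |

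**Step 4: does replacement help?** It can restore the count but not the lost patients. To end with 40 observed FD patients, 40/0.8 = 50 to 40/0.7 = 57.1, so 58, would have to be treated. If replacements are lost at the same rate, the missing share d is still 20% to 30%, and the ratios in step 3 do not change.

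**The case against.** The case against has real substance.

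- **A reader might infer that the analysis is completers-only.** The documents do not support that. Protocol 6.4 brings in early stoppers who are assessed at discontinuation, and Protocol 6.6 allows unscheduled visits. The accurate term is observed cases. The safeguard has limits: Protocol section 4 makes no stipulations on visits or assessments, the Patient Confidentiality text in section 6 ends data collection when a patient ends participation, and patients lost to contact are not reached.
- **A reader might infer that 20% to 30% FD loss is the plan's settled rate.** It appears only in the summary. At the 10% in Protocol section 8 and SAP 5.1, the loss is 4 of 40 and the zero-change ratio is 0.90.
- **A reader might infer that the improvement will be overstated.** Patients without benefit may stay away, but so may patients who have recovered. Nothing in the documents settles this, and the f = 1.5 column shows the opposite direction.
- **A reader might infer that replacement will happen.** It is optional and limited by date.
- **Exclusions are not hidden.** The definition is stated openly, and Tables 14.1.2 and 14.1.3 report early termination and reasons for exclusion. The study is descriptive, so there is no type I error or randomised comparison to damage.

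All of this narrows the point without removing it. A descriptive study still reports intervals meant to estimate treatment effects, and counts of exclusions do not show whether the excluded patients differed.

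**Conclusion.** The point holds as one of labelling and of an unexamined missing-data risk. The effectiveness set is an observed-case or modified ITT set, and treated patients with no post-baseline measurement are left out of the effectiveness tables and out of the main baseline tables.

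The size depends on which loss rate applies. If lost patients had zero change, the all-treated mean would be 0.90 (10% loss) or 0.80 to 0.70 (20% to 30% loss) of the observed mean in FD, and 0.90 in BVP. With half the observed change it would be 0.95, or 0.90 to 0.85, in FD and 0.95 in BVP. These ratios rest on assumed outcomes and on no recovery of lost patients through a discontinuation visit. They illustrate sensitivity and do not estimate bias. The changes are inexpensive and worth making.

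**What to change.** 1. Rename the set *observed cases* or *modified ITT* in SAP 5.5 and the tables. For the DHI change analysis, require a baseline and a post-baseline DHI total.
2. Tabulate demographics, diagnosis and baseline DHI total for the Safety population, split by follow-up DHI available yes/no, and flag replaced patients. Do this as far as consent allows: under Protocol section 6, a patient who refuses further use has the data deleted.
3. Add to Table 14.2.1 the mean DHI total change with 95% CI, by FD and BVP. The DHI total is the primary endpoint in the Observational Plan Summary, but the table entry lists only answer categories and a shift table. Then add a sensitivity row, labelled as such, for all treated patients with zero change assigned to those without a follow-up DHI.
4. Reconcile the 10% and the 20% to 30% loss rates between the Observational Plan Summary, Protocol section 8 and SAP 5.1.

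The cost is SAP wording and a few table rows; no new visits or data are needed. The drawback is that zero change is one arbitrary assumption and not a worst case, because lost patients could have worsened. The row must therefore stay a sensitivity result and not replace the main estimate.

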5.6 Definitions

5.6.1 Definition of Baseline

Baseline is defined as Screening Visit.

5.6.2 Absolute change from Baseline

Absolute change from baseline = post-baseline value – value at baseline.

5.6.3 Age

Age at baseline is derived as years of baseline – years of birth.

5.6.4 First patient in, last patient out

First patient in is defined as earliest date of Screening Visit.

Last patient out is defined as last date of Visit 1 and Unscheduled Visit.

1. Appendices

Appendix 1: Tables, Listings, Figures

Item No.	Title	Population	Content Description
14.1	Disposition, Baseline Characteristics, Medication and Further Analyses		
14.1.1	Patient disposition	All	Descriptive statistics on patients screened, failed screening, treated
14.1.2	Early termination	All	Descriptive statistics for early termination yes/no
14.1.3	Number of patients in each analysis population	All	Descriptive statistics for number and percentage of patients and reason for exclusion
14.1.4	Duration of study	All	Date of first patient in and last patient out of all patients
14.1.5	Duration of observation per patient	SP	Difference of Date of patient in and patient out per patient
14.1.6	Demographics and other baseline characteristics	ITT	Descriptive statistics of age, , height, weight, pregnancy test
14.1.7.1	Vital signs	ITT	Descriptive statistics of heart rate and blood pressure, at Screening Visit and 2±1 month after baseline
14.1.7.2	Physical examination	ITT	Descriptive statistics (normal, abnormal, ncs (not clinically significant), cs (clinically significant)), at Screening Visit and 2±1 month after baseline (shift table)
14.1.8.1	Primary diagnosis	ITT	Descriptive statistics of 
 - FD yes/no (derived from tick box 'NA' for caloric (BVP)) - BVP yes/no (derived from tick box 'NA' for GAD-7 (FD))
14.1.8.2	Medical history - Abuse history	ITT	Descriptive statistics of alcohol and drug consumption, smoking status
14.1.9.1	Treatment with Vertigoheel	SP	Descriptive statistics for 
 - Duration of treatment (date start of study – date start of Vertigoheel treatment - change of Vertigoheel dose yes/no
14.1.9.2	Prior medication	SP	Descriptive statistics for prior medication yes/no
14.1.9.2	Concomitant medication	SP	Descriptive statistics for change of concomitant medication yes/no
14.1.9.3	Product complaints	SP	Descriptive statistics for product complaint yes/no

14.2	Patient Reported Outcomes (Effectiveness)		
14.2.1	Primary Endpoint		
14.2.1	Dizziness Handicap Inventory	ITT	Descriptive statistics at Screening Visit and 2±1 month after baseline (yes, sometimes, no), and change from baseline to 2 months (shift table)
14.2.2	Secondary Endpoints		
14.2.2.1	Posturography	ITT	Descriptive statistics at Screening Visit and 2±1 month after baseline (normal, neuritis vestibularis, PPV), and change from baseline to 2±1 month after baseline (shift table)
14.2.2.2	Quality of Live (EQ-5D-5L)	ITT	Descriptive statistics per question, at Screening Visit and Visit 1, and change from baseline to 2 months
14.2.2.3	Patient Health Questionnaire depression module (PHQ-9)	ITT In patients with FD	Descriptive statistics for total score, at Screening Visit and Visit 1, and change from baseline to 2 months
14.2.2.4	Generalized anxiety disorder scale (GAD-7)	ITT In patients with FD	Descriptive statistics for total score, at Screening Visit and Visit 1, and change from baseline to 2 months
14.2.2.5	Video head impulse test (vHIT)	ITT In patients with BVP	Descriptive statistics at Screening Visit and Visit 1 (not done, normal, pathologic), and change from baseline to 2 months (shift table)
14.2.2.6	Caloric testing	ITT In patients with BVP	Descriptive statistics per parameter, at Screening Visit and Visit 1, and change from baseline to 2 months

14.3	Safety Analyses		
14.3.1	Adverse Events		
14.3.1.1	Overview of adverse events	SP	Number and percentage of patients with adverse events (yes/no), intensity (mild, moderate, severe), causality (related, not related, unknown)

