## **OBSERVATIONAL PLAN SUMMARY**

Title of Observational Study	Evaluation of the impact of Vertigoheel ® on patients suffering from bilateral vestibulopathy and functional dizziness in a real- world setting, using patient reported outcomes and quality of life of patients
Type of Study	Non-interventional observational study.
Rationale	Vertigo is a common symptom with significant adverse effects on patients' QoL. Regardless of the exact cause of vertigo attacks, it is important to reduce the frequency, intensity, and duration of vertigo attacks with an effective medication that has no or minimal adverse effect. Vertigoheel ® , a natural medicinal product consisting of four ponderable active ingredients, is approved in Germany by BfArM as treatment for vertigo of various origins. However, no systematic data is available for Vertigoheel ® regarding patient-reported outcomes in bilateral vestibulopathy and functional dizziness as the most accepted endpoint in vertigo studies in which also German health insurance are interested. Therefore, patient-reported outcomes (PRO) as well as quality of life (OoL) assessed during clinical practice, were chosen as primary and secondary objectives respectively, to evaluate symptoms and QoL of Vertigoheel ® -patients in Germany.
Exposure and Outcome	Patients treated with Vertigoheel ® will occur according to SmPC and will be observed with respect to change in PRO, postural imbalance and QoL.
Duration of Observation	It is planned to observe patients treated with Vertigoheel ® for a duration of 2 months.
Primary Objective	• To evaluate the change from baseline in PRO after 2±1 months of routine Vertigoheel ® treatment for patients suffering from functional dizziness (FD) and bilateral vestibulopathy (BVP).
Secondary Objectives	
 
To evaluate the change from baseline in QoL after 2±1 month of routine Vertigoheel® treatment measured by questionnaires.
 
To evaluate the change from baseline in postural imbalance after 2±1 months of routine Vertigoheel® treatment for patients suffering from FD and BVP.
 
To evaluate the change from baseline in psychiatric symptoms after 2±1 months of routine Vertigoheel® treatment for patients suffering from FD measured by questionnaires.
 

Drimory Frederainta	
Primary Endpoints	• Effect of Vertigoheel ® on subjective symptoms of the

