## 5 STUDY FLOW CHART

Procedure	Visit 0 Month 0 Baseline	Visit 1 Month 2 +/- 1 after Baseline			
Evaluations / Recordings					
Patient informed consent	X				
Assignment of patient number	Х				
Inclusion/exclusion criteria	Х				
Physical examination including vital signs (heart rate, blood pressure)	Х	Х			
Demographics, from Visit 1 documentation of changes vs. baseline for variable demographic parameters	Х	Х			
Medical and medication history vertigo-related	X	X			
Concomitant diseases/medications	Х	х			
Procedure (continued)					
Evaluations / Recordings					

DHI	Х	Х			
Posturography	х	Х			
FD: PHQ-9, GAD-7	х	Х			
BVP: vHIT, caloric testing	х	Х			
Quality of life (EQ-5D-5L)	х	х			
Review of Vertigoheel administration	х	Х			
Adverse events / Serious Adverse Events		X			
Patients who stopped therapy		Х			
(reasons for d/c, date of last intake)					
		Close Out			
		Documentation			

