2 OBJECTIVES

2.1 Primary Objectives

- To evaluate the change in PRO 2±1 month after baseline versus baseline for patients suffering from functional dizziness (FD) and bilateral vestibulopathy (BVP) treated with Vertigoheel® in German clinical practice.

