2.2 Secondary Objectives

- To evaluate the change from baseline in QoL after 2±1 month of routine Vertigoheel® treatment measured by questionnaires
- To evaluate the change from baseline in postural imbalance after 2±1 month of routine Vertigoheel® treatment for patients suffering from FD and BVP
- To evaluate the change from baseline in psychiatric symptoms after 2±1 month of routine Vertigoheel® treatment for patients suffering from FD measured by questionnaires

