3 METHODOLOGY

3.1 Study Design

This study is an open-label, prospective, monocenter non-interventional study. It is set up for descriptive purposes.

All study activities are consistent with the EU Directive 2001/20/EC section for non-

interventional studies as follows:

- The study drug is prescribed in the usual manner in accordance with the terms of the marketing authorization/SmPC.
- The assignment of the patient to a particular therapeutic strategy is not defined by the observational plan but falls into the responsibility of the treating physician.
- No extra means of interventions that would not otherwise be used, will be applied to the patients.

Patients are observed for 2±1 month under Vertigoheel® treatment.

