4 STUDY FLOW CHART

Procedure	Visit 0 Month 0 Baseline	Visit 1 Month 2 +/- 1 after Baseline						
Evaluations / Recordings								
Patient informed consent	x							
Assignment of patient number	x							
Inclusion/exclusion criteria	x							
Physical examination including vital signs (heart rate, blood pressure)	x	x						
Demographics, from Visit 1 documentation of changes vs. baseline for variable demographic parameters	x	x						
Medical and medication history vertigo-related	x	x						
Concomitant diseases/medications, from Visit 1 documentation of changes vs. baseline	x	x						
Procedure (continued)								
Evaluations / Recordings								

DHI		x	x			
Posturography		x	x			
FD: PHQ-9, GAD-7		x	x			
BVP: vHIT, caloric testing		x	x			
Quality of life (EQ-5D-5L)		x	x			
Review of Vertigoheel administration		x	x			
Adverse events / Serious Adverse Events			x			
Patients who stopped therapy (reasons for d/c, date of last intake)			x			
		Close Out Documentation				

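### No listed SAP table shows time on Vertigoheel or why patients stopped, so the report cannot say how many two-month values follow 2±1 months of treatment

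*SAP*

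**What the plan says.** **Objectives.** The Observational Plan Summary words the primary objective by time on treatment: "To evaluate the change from baseline in PRO after 2±1 months of routine Vertigoheel". The secondary objectives do the same (Protocol 2.2 and SAP 2.2), for example "To evaluate the change from baseline in QoL after 2±1 month of routine Vertigoheel® treatment measured by questionnaires". SAP 3.1 adds: "Patients are observed for 2±1 month under Vertigoheel® treatment". The primary objective in SAP 2.1 is worded by time since baseline: "To evaluate the change in PRO 2±1 month after baseline versus baseline for patients suffering from functional dizziness (FD". Protocol 2.1 has the same sense.

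**Data collected.** The Visit 1 column of the protocol flow chart (section 5) includes, for patients who stopped therapy, "reasons for d/c, date of last intake". The SAP flow chart (section 4) repeats the item: "Patients who stopped therapy (reasons for d/c, date of last intake".

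**Planned outputs (SAP Appendix 1).**
- 14.1.2: "Descriptive statistics for early termination yes/no".
- 14.1.5: each patient's time between entering and leaving the study.
- 14.1.9.1: duration of treatment, defined as the start date of the study minus the start date of Vertigoheel, and whether the dose changed.
- 14.2.1 and 14.2.2.2 to 14.2.2.6: effectiveness results, described as change to 2 months.

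**Populations.** Effectiveness is analysed in the ITT set of SAP 5.5: "all patients who have received at least one dose of Vertigoheel", provided they also have a post-baseline measurement. There is no per-protocol set. SAP 5.4 allows no subgroups other than FD and BVP.

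**Assessment of patients who stop.** Protocol 6.4 (Termination of Vertigoheel treatment) has the final-visit activities done when the patient discontinues. Protocol 6.6 (End of follow-up) ends follow-up at month 2±1, death or withdrawal of consent, and does not list stopping the drug.

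**The concern.** Several objectives are framed by duration of treatment. The effectiveness tables require one dose and one later measurement, with no minimum exposure. That would be acceptable if the report also showed how long patients took the drug and why some stopped, and the CRF is set up to collect both facts. The table list then drops them.

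Two things are at stake. First, a reader cannot judge how far a two-month change describes patients who had 2±1 months of treatment. Second, in a single-arm study the reasons for stopping (lack of effect, an adverse event, recovery) are direct information on effectiveness and tolerability, and the listed tables do not report them.

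**Working it through.** The plan has no figure of its own to reproduce here: it states neither a stopping rate nor an expected time on drug. Its precision calculation (half-width 0.351 at n = 20) uses only the SD and n, and does not bear on this point.

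**Step 1. Does any listed table recover time on drug or the reason for stopping?**

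| Item | Uses date of last intake? | Uses reason? |
|---|---|---|
| 14.1.1 Disposition (screened, failed screening, treated) | no | no |
| 14.1.2 Early termination, yes/no | no | no |
| 14.1.5 Time in study | no | no |
| 14.1.9.1 Duration of treatment | no | no |

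Item 14.1.9.1 looks like the natural place, but its formula contains no stop date. Recent and current users are excluded (SAP 3.5), so an eligible patient starts Vertigoheel at or after study entry. If treatment starts on the day of entry, the formula gives 0 − 0 = 0 days. If it starts one day later, it gives 0 − 1 = −1 day. The result is the same whether the patient took tablets for 3 days or for 2 months.

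**Step 2. Where does a stopper's value go?** There are two routes.
- Under Protocol 6.4 the final assessment is done at discontinuation. The value then follows a short exposure and may fall before the month 2±1 window.
- Under Protocol 6.6 stopping does not end follow-up, so a patient may also be assessed at Visit 1, off the drug.

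Either value satisfies the ITT definition and enters the tables described as two-month change. The SAP gives no rule for either, nor for a patient who has both.

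**Step 3. How large could the effect be?** All inputs here are assumptions. Let s be the share who stopped but were measured, and let M_on and M_stop be the mean DHI changes in the two groups.

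Pooled mean = (1 − s) × M_on + s × M_stop, so pooled mean − M_on = s × (M_stop − M_on).

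- Assume s = 10% to 30%. BVP: 0.10 × 20 = 2 to 0.30 × 20 = 6 patients. FD: 0.10 × 40 = 4 to 0.30 × 40 = 12 patients.
- Assume the groups differ by 10 DHI points. The shift is 0.10 × 10 = 1 point to 0.30 × 10 = 3 points, on a 0–100 scale.

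If stoppers instead show a fraction r of the on-drug change, pooled mean / M_on = 1 − s × (1 − r):

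| s | r = 0 | r = 0.5 | r = 1 |
|---|---|---|---|
| 10% | 0.90 | 0.95 | 1.00 |
| 20% | 0.80 | 0.90 | 1.00 |
| 30% | 0.70 | 0.85 | 1.00 |

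If patients stop because they have improved, r exceeds 1 and the shift reverses.

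The 10–30% range is borrowed from the loss-to-follow-up figures in the protocol summary (10% BVP, 20% to 30% FD); SAP 5.1 has 10%. Those figures describe patients lost before a final value, not stoppers who have one. For BVP the documents give only 10%, so the upper figure of 6 of 20 goes beyond anything stated.

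**The case against.** The strongest reply is that analysing every treated patient with a later measurement is a legitimate treatment-policy choice in a descriptive study, and that it fits the primary objective as SAP 2.1 words it. SAP 5.5 also gives a reason for having no per-protocol set: routine care, with no stipulated visits. All of this stands. A reader might infer that the main analysis is wrong or should be restricted to patients still on the drug. The documents do not support that, and such a restriction would select on a post-baseline event probably related to response.

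A second reply is that SAP 3.3 promises a descriptive analysis of treatment intervals and dosage, SAP 5.3.9 lists administration details and early termination, and SAP 5.4 promises descriptive statistics for all parameters. These are general statements. The table list meant to carry them out names neither last intake nor reason, and its duration formula cannot give exposure. A by-patient listing cannot be ruled out, since the SAP introduction mentions listings and the available appendix text itemises none. It would not replace a summary.

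Two stronger readings are tempting and go too far:
- A reader might infer that patients off the drug are counted as treated for two months. The SAP does not say so. Under Protocol 6.4 the value may be an early one taken at discontinuation, not an off-drug one.
- A reader might infer that 14.1.2 merges stopping the drug with leaving the study. Early termination is undefined, so this is possible but not shown.

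**Conclusion.** The point holds as a reporting gap, not as an error in the main analysis. Reason for stopping and date of last intake are collected and appear in no listed table, and the one planned measure of treatment duration cannot measure it. The report could therefore not show how many two-month values follow 2±1 months of treatment, or why other patients stopped.

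The objectives at issue are the primary one as worded in the protocol summary, and the secondary ones. The primary objective in Protocol 2.1 and SAP 2.1 refers only to time since baseline.

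Size and direction are unknown because the documents give no stopping rate. The shift of 1 to 3 DHI points rests wholly on the assumed 10–30% share and 10-point difference, and it is not shown to be clinically important. The case for acting is that the change is cheap and the data are already planned for collection.

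**What to change.** 1. **Replace 14.1.2** with counts by diagnosis: stopped the drug and assessed at discontinuation; stopped the drug and assessed at month 2±1; withdrew consent; lost to follow-up. Give the recorded reason for each, and define early termination.
2. **Redefine duration of treatment in 14.1.9.1** as first to last intake.
3. **Keep the all-treated analysis as the main one**, and state that it includes patients regardless of stopping. State how values taken at discontinuation before the month 2±1 window are handled, since a label of month 2±1 would be false for them. Protocol 6.4 and 6.6 leave open when a patient who stops is assessed. The authors need to reconcile them so that the rule can be written.
4. **Add to 14.2.1 a descriptive row** for change in DHI total with its 95% CI, by status at assessment (on drug or stopped), derived from the date of last intake.

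**Cost.** SAP wording and a few table rows, with no new data collection. SAP 5.4 would need an exception to its statement that no further subgroups are defined. The on-drug row is selected on a post-baseline event and the stopped row will be small, especially in BVP, so both should be labelled supportive only.
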